4.6.2. Potentially Clinically Important Laboratory Values

Potentially clinically important (PCI) laboratory values are presented in Table 8 below:

Table 8: Potentially Clinically Important Laboratory Criteria

Analyte	PCI Low: Less than or equal to	PCI High: Greater than or equal to
Hemoglobin (g/L)	100	190
Hematocrit	0.3	0.6
Platelets ($10^9/L$)	100	650
ALT (U/L)		$3 \times \text{ULN}$
AST (U/L)		$3 \times \text{ULN}$
Creatinine ($\mu\text{mol/L}$)		300
BUN (mmol/L)		12

ALT=Alanine transaminase; AST=Aspartate transaminase; BUN=Blood urea nitrogen; ULN=Upper limit of normal

4.6.3. Potentially Clinically Important Vital Sign Values

Vital sign values are PCI if they meet both the observed value criteria and the change from baseline criteria. The PCI vital sign values are presented in [Table 9](#) below:

Table 9: Potentially Clinically Important Vital Sign Criteria

Parameter	PCI Low	PCI High
Systolic blood pressure	≤ 90 mmHg and decrease ≥ 20 mmHg from baseline	≥ 180 mmHg and increase ≥ 20 mm Hg from baseline
Diastolic blood pressure	≤ 50 mmHg and decrease ≥ 15 mmHg from baseline	≥ 105 mmHg and increase ≥ 15 mmHg from baseline
Pulse rate	≤ 50 bpm and decrease ≥ 15 bpm from baseline	≥ 120 bpm and increase ≥ 15 bpm from baseline
Respiratory rate	≤ 8 brpm and decrease ≥ 7 brpm from baseline	≥ 25 brpm and increase ≥ 7 brpm from baseline
Temperature		$\geq 38.3^{\circ}\text{C}$ and increase $\geq 1.1^{\circ}\text{C}$ from baseline

bpm=Beats per minute; brpm=Breaths per minute

4.7. Immunogenicity

Seropositivity and titer levels for both anti-AUX-I and anti-AUX-II antibodies will be obtained from each analyzed sample. Samples with a positive titer value will undergo a log transformation for analyses. Samples with titer level less than 1 will be assigned or imputed as a log transformed titer of zero (0) for analyses.

All samples with seropositive antibodies will be tested for neutralizing antibodies. Samples will be classified as positive or negative for neutralizing antibodies based on the results of these analyses.

The immunogenicity profiling will be performed only if clinical findings and/or PK results warrant immunogenicity profiling.

5. ANALYSIS POPULATIONS

The study will use the following analysis populations for data summarization.

Table 10: Analysis Populations

Population	Definition	Displays
Safety Population	The Safety Population includes all enrolled subjects who received at least one injection of CCH.	All demographic, baseline characteristics and safety parameters will be summarized based on this population.
Pharmacokinetic (PK) Population	The PK Population includes all enrolled subjects who received the full dose of CCH and have sufficient data from the 24-hour PK profile to determine key PK parameters such as C_{max} and AUC_{0-t} .	The plasma concentration of AUX-I and AUX-II as well as PK parameters will be summarized based on this population.
Cellulite Severity Population	The Cellulite Severity Population consists of all enrolled subjects who receive at least one injection of CCH and have the screening and Day 22 CR-PCSS evaluation completed.	All summaries of cellulite severity, including changes from baseline, will be based on this population.

6. STATISTICAL METHODS

6.1. General Methodology

All summary tables and data listings will be prepared using SAS version 9.4.

Continuous data will be summarized using descriptive statistics. Discrete data will be summarized using frequency counts and percentages. The denominator will be based on the number of subjects. For the purpose of display, the summary results will be rounded as follows:

- Min and max: same number of decimal places as the raw data.
- Mean and median: one more decimal place than the raw data.
- SD: two more decimal places than the raw data.
- Percentages will be displayed with precision to one decimal place. A zero count will not have the associated percentages presented on the table (ie, no 0%). It will be left blank.
- The standard form of a percent change variable is 0 decimal places.

For categorical variables with missing values, a category documenting the frequency of missing values will be displayed in the summary tables.

Summary tables, subject listings, graphs and any supportive SAS output will include a footnote that will indicate, when applicable:

- Date of data extraction
- Date and time of output generation
- SAS program name, including the path, that generates the output

When calculating percentages, the denominator will be based on the number of subjects with non-missing values. If the denominator is expected to change over time, then the denominator used to calculate the percentages should be based on the number of subjects with non-missing values at each visit. Any subject removed from an analysis will be noted at the bottom of the table along with the reason the subject was removed.

Null summary tables will be presented with a note stating that “No Subjects Met Criteria.”

Subject listings of all data from the eCRFs as well as any derived variables will be presented.

6.2. Derived Variables

Refer to [Table 11](#) for the listing of the derived variables and their definitions for study parameters.

Table 11: Derived Variables and Definition

Variable	Definition
Height (cm)	If height is recorded in inches, then height is equal to the recorded value multiplied by 2.54 and then rounded to 1 decimal point.
Weight (kg)	If weight is recorded in pounds, then weight is equal to the recorded value multiplied by 0.454 and then rounded to 1 decimal point.
Body Mass Index (BMI)	BMI will be computed using height and body weight measured at screening as, $BMI \text{ (kg/m}^2\text{)} = \text{Weight (kg)} / \text{Height (m)}^2$
Relative Day	The day of first injection of study drug will be considered as relative day 1
Study Day (for assessment on or after the Day 1)	Study Day will be computed as, Date of Assessment – Date of Day 1 + 1
Study Day (for assessment before Day 1)	Study Day will be computed as, Date of Assessment – Date of Day 1
Baseline	Baseline is defined as the last non-missing measurement/assessment prior to the first dose of study drug. For vital signs, the baseline will be the Day 1 pre-dose values. For clinical laboratories this could be the screening value, or it could be an unscheduled lab, if the unscheduled lab is the closest value preceding the first injection.
Change from Baseline	Change from baseline will be derived as, post-baseline visit/time point value – the baseline value.
Last Date in Study	End date of last visit where subject was seen by investigator. If subject was lost to follow-up, then last date of contact. If the subject had contact with the site after the final visit (eg, to follow-up on an AE), the last visit date will still be used as last date in the study.
Time in Study	Last date in study – Date of first injection + 1
Age at EFP Symptom Onset	Date of EFP symptoms reported – Date of Birth/365.25. See section 6.3.1.3 for handling of partial or unknown EFP symptom onset dates.
Time since last EFP treatment	Date of most recent EFP treatment – Date of informed consent)/365.25. See section 6.3.1.3 for handling of partial or unknown EFP treatment dates.
Baseline CR-PCSS Score	Investigator baseline CR-PCSS scores for each quadrant will be based on the investigator's CR-PCSS evaluation done at the Screening visit.
Change from Baseline CR-PCSS Score	The change from baseline CR-PCSS score at each quadrant will be the Day 22 score minus the baseline (Screening visit) score. A negative change indicates an improvement of cellulite severity in the treated quadrant.
Nominal time of PK blood sample collection	Pre-injection=0 hr, 5 min post injection=0.083 hrs, 10 min post injection=0.167 hrs etc.
Time difference of blood draw from last injection (hours)	Date/time of sample draw - Date/time of last injection
Duration of AE	AE end date – AE start date + 1
AE Onset Day	AE start date - Date of first injection + 1
Creatinine clearance (estimated) (eCrCl)	Creatinine clearance will be estimated by Endo using the Cockcroft-Gault formula (see [2]) as: $\text{eCrCl (mL/min)} = \{(140-\text{age}) \times \text{weight}\} / (72 \times \text{SCr}) \times 0.85 \text{ for female}$ where, age is expressed in years (yrs), weight is expressed in kilograms (kg), and serum creatinine (SCr) is expressed in milligrams per deciliter (mg/dL).

6.3. Handling of Missing Data

Subjects who discontinue the study prior to or after the initiation of the study drug will not be replaced and available data for these subjects until the point of discontinuation will be summarized. Any missing baseline assessments will not be imputed.

For categorical variables with missing values, a category documenting the frequency of missing values will be displayed in the summary tables.

Subjects who discontinue early will be requested to complete all Day 22 procedures and assessments at an early termination visit.

There will be no imputation of missing values for safety data, however missing relationship between AE and study drug will be considered as related to study drug following the WOCF rule. Missing severity of an AE will be summarized as a severe AE.

Samples with a positive titer value for both anti-AUX-I and anti-AUX-II antibodies will undergo a log transformation for analyses. Samples with titer level less than 1 will be assigned or imputed as a log transformed titer of zero (0) for analyses.

All plasma concentration values below the limit of quantification (BLQ) will be set to zero (0) in calculation of summary statistics. If the plasma concentration levels are BLQ for all subjects at a time point, then Not Calculable (NC) will be reported in the summary table. Any missing samples will be reported as 'Missing' and treated as missing for PK parameter and plasma concentration summary calculations. C_{max} , AUC_{0-t} , AUC_{0-inf} will be imputed as 0 and Terminal rate constant and T_{max} will be imputed as 'missing' when all plasma concentrations are below lower limit of quantifications.

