
Criteria for evaluation:
 
Safety: The safety of CCH will be evaluated through the collection of adverse events (AEs), including a targeted assessment of local/systemic reactions to the dose. Vital sign measurements and clinical laboratory testing will also be performed.
 
Pharmacokinetics: Subjects will have blood samples collected for the determination of plasma AUX-I and AUX-II concentrations before dosing and 5, 10, 20, and 30 minutes, then at 1, 2, 4, 8, 12, and 24 hours after dosing while confined to the research unit. Subjects will return for PK blood draws at 48 (Day 3), 168 (Day 8), and 504 (Day 22) hours post dose on an outpatient basis. All blood samples are to be collected within 10% of the nominal time.
 
The following PK parameters will be determined for each subject who has quantifiable plasma concentrations at any time during the 504-hour period following the last injection: maximum drug concentration (C_{max}), time to maximum drug concentration (T_{max}), area under the plasma concentration time curve from time of dosing (0) to the time of last quantifiable concentration (AUC_{0-t}), and area under the plasma concentration time curve from time of dosing (0) to infinity (AUC_{0-inf}).
 
Immunogenicity: Blood samples will be collected pre-dose on Day 1 and on Day 22 after dosing for possible determination of anti-AUX-I and anti-AUX-II antibodies in serum; assay of these samples will be conducted only if clinical signs and/or PK results warrant determinations. Descriptive statistics (percent positive measurements and average antibody level) will be calculated for anti-drug antibody titers at each visit if antibody determinations are conducted.
 
Cellulite Severity Evaluation: Cellulite will be assessed by the Investigator's rating of cellulite severity using the CR-PCSS at the Screening visit and on Day 22.

Name of Sponsor/Company: Endo Pharmaceuticals Inc.
Name of Investigational Product: CCH
Name of Active Ingredient: Collagenase clostridium histolyticum
Statistical methods:
Sample Size Consideration: No formal sample size calculations were performed. Completion of 10 subjects will provide sufficient data to meet the PK study objectives.

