Cellulite Severity Analysis: Evaluations will be done on the quadrants using the CR-PCSS at Screening and Day 22. Change from baseline in cellulite severity will be computed. The Screening and Day 22 ratings will be summarized with counts and percentages at each level of severity and with mean and standard deviation (SD). The change from baseline value will be summarized with counts and percentages at each possible change value and with mean and SD. The cellulite severity population will be used to summarize the cellulite severity data.
Pharmacokinetic Analysis: PK data will be summarized through data tabulations, descriptive statistics, and graphic presentations, as appropriate. Actual blood sampling times will be used in all PK analyses. AUC_{0-t} , AUC_{0-inf} , and C_{max} will be summarized with descriptive statistics (number, mean, SD, median, minimum, and maximum) as well as the geometric mean and coefficient of variation (CV). Geometric means and CV will be calculated for the log transformed parameters, using the following SAS formula:
$CV (\%) = \text{SQRT}[\exp(\text{SD}^2)-1] * 100$
T_{max} will be summarized with descriptive statistics (number, mean, SD, median, minimum, and maximum) only.
If all subjects have all PK concentrations below the limit of quantification (BLQ), then all PK parameters will be summarized as not calculable.

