7.8.2. Pharmacokinetic Parameters

AUC_{0-t} , AUC_{0-inf} , C_{max} and T_{max} will be summarized using descriptive statistics for the PK Population. In addition, the geometric mean and coefficient of variation (CV) will be calculated and presented for AUC_{0-t} , AUC_{0-inf} , and C_{max} . Geometric means and CV will be calculated for the log transformed parameters. The CV will be calculated as:

$$CV (\%) = \text{SQRT}[\exp(\text{SD}^2) - 1] * 100$$

The handling of missing and BLQ data is described in section [6.3](#). Individual AUX-I and AUX-II PK parameters will be listed.

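### SAP 6.3 sets Cmax and both AUCs to 0 when all concentrations are BLQ, but SAP 7.8.2 log-transforms them: in a mixed data set the geometric mean and CV cannot be computed, and the zero rule is an undeclared departure from the protocol

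*SAP*

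**What the plan says.** SAP 6.3 states that Cmax, AUC0-t and AUC0-inf "will be imputed as 0 and Terminal rate constant and" Tmax as missing "when all plasma concentrations are below lower limit of quantifications". The sentence does not say whether it applies per subject. These parameters are derived subject by subject, so that is the natural reading.

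SAP 7.8.2 requires descriptive statistics for the parameters in the PK Population. For AUC0-t, AUC0-inf and Cmax it adds: "Geometric means and CV will be calculated for the log transformed parameters". On BLQ data it says only: "The handling of missing and BLQ data is described in section" 6.3.

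SAP 6.3 contains two neighbouring rules. One is an NC rule for concentrations: if levels are "BLQ for all subjects at a time point, then Not Calculable (NC) will be reported in the summary table". The other is a log-scale rule for antibodies: "Samples with titer level less than 1 will be assigned or imputed as a log transformed titer of zero (0) for analyses". Neither covers a PK parameter equal to 0.

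The protocol differs in two places. Its Synopsis says that "PK parameters will be determined for each subject who has quantifiable plasma concentrations at any time during the 504-hour period following the last injection". The Synopsis also says, and section 16.7.3 repeats in substance: "If all subjects have all PK concentrations below the limit of quantification (BLQ), then all PK parameters will be summarized as not calculable". SAP 8 states that no change to the planned analysis is intended, and Table 12 lists none.

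**The concern.** Followed literally, the SAP puts zeros into a calculation that cannot accept them. A programmer would have to choose, without written guidance, whether to drop the zeros, replace them with a small value, or print NC for the whole statistic. That choice would be made after the data are in hand, and it changes the figures printed.

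Determining whether there is systemic exposure is a primary objective, and this is the parameter table that describes it. All-BLQ subjects are also to be expected: Protocol 8.2.1 reports no quantifiable level in 93, 11 and 17 evaluable subjects in three earlier EFP studies.

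The second strand is the match with the protocol. The protocol determines no parameters for a subject who is never quantifiable, while the SAP assigns that subject three values of 0. Where every subject is all BLQ, the protocol reports the parameters as NC, while SAP 6.3 read literally gives arithmetic means of 0. Neither difference is declared.

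**Working it through.** There is no stated figure to reproduce: the sample size of 12 has no formal calculation, and the point concerns rules.

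**Step 1. Apply the rules to each data pattern, for one analyte.** The log-scale statistics are GM = exp(mean of ln x) and CV% = sqrt(exp(SD²) − 1) × 100, with SD on the ln scale.

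| Pattern | SAP 6.3 gives | Log-scale result | Rule that settles it |
|---|---|---|---|
| No subject all BLQ | no zeros | computable | none needed |
| Mixed | at least one zero | ln(0) undefined, so GM and CV are not computable | none in the SAP |
| Every subject all BLQ | all zeros | not computable | protocol NC rule, not repeated in the SAP for parameters |

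One zero among 12 values is enough. It affects 3 parameters × 2 statistics = 6 table cells for that analyte, or 12 cells if it happens for both AUX-I and AUX-II. Software that treats ln(0) as minus infinity returns a GM of 0 and no CV, which is no more usable.

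**Step 2. Chance of the unresolved (mixed) pattern.** Let p be the per-subject chance of at least one quantifiable level, with independent subjects. Then P(mixed) = 1 − (1 − p)^n − p^n.

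The rates are assumptions. To place them: the one-sided 95% upper limit after 0 of m is 1 − 0.05^(1/m). This gives 23.8% for 0 of 11 (one quadrant), 16.2% for 0 of 17 (two quadrants) and 10.1% for the pooled 0 of 28. This study treats four quadrants, so the earlier rates need not carry over.

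| Assumed p | All BLQ, n=12: (1 − p)^12 | Mixed, n=12 | Mixed, n=10 |
|---|---|---|---|
| 1% | 0.8864 | 0.1136 | 0.0956 |
| 5% | 0.5404 | 0.4596 | 0.4013 |
| 10% | 0.2824 | 0.7176 | 0.6513 |
| 24% | 0.0371 | 0.9629 | 0.9357 |

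The p^n term is negligible throughout this table. At p = 0, P(mixed) = 0.

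**Step 3. What the unwritten choice does.** As an illustration with assumed values, let Cmax be 10, 15, 20 and 28 ng/mL in 4 of 12 subjects, with the other 8 all BLQ.

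- Zeros kept: arithmetic mean = 73/12 = 6.08; GM and CV undefined.
- Zeros dropped from the log statistics: GM = (10 × 15 × 20 × 28)^(1/4) = 17.0, CV 46%, both on n = 4.
- Zeros replaced by an assumed 1, 2.5 or 5 ng/mL: GM 2.6, 4.7 or 7.5; CV 253%, 125% or 72%, on n = 12.

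The same data therefore give a GM anywhere from 2.6 to 17.0, or none, depending on a choice that the SAP does not make.

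**The case against.** The strongest reply is that the expected outcome is already covered. If no subject is quantifiable, as in the earlier EFP studies, the protocol's NC rule applies, and because SAP 8 declares no changes that rule can be taken to stand. This is right. A reader might infer that the parameter table is bound to fail on the expected data, because at least one all-BLQ subject is nearly certain. The documents do not support that: the event that matters is the mixed data set, whose chance is 0 when the quantifiable rate is 0. What remains is the mixed case, plus an SAP sentence that contradicts the NC rule if read alone.

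Secondly, SAP 6.1 requires a table footnote for any subject removed from an analysis, with the reason. Dropping zeros would therefore not go unreported. But that rule discloses a choice; it does not make one.

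Thirdly, the PK Population needs enough 24-hour data to determine key parameters, which could be read as excluding all-BLQ subjects. The zero rule would then have no use in the summaries it was written for. If 6.3 instead refers to all subjects together, it conflicts directly with the protocol's NC rule.

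Finally, SAP Module 2 holds the table layouts and footnotes and was not available. It may show n for each statistic or NC. If so, the Module 1 text still has to agree with it.

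**Conclusion.** The point holds and is minor. SAP 6.3 and 7.8.2 cannot both be carried out on a mixed data set, and the zero rule departs from the protocol without being declared. With 12 subjects, the chance of a mixed data set is about 11% to 96% for assumed quantifiable rates of 1% to 24%. This treats subjects as independent and counts one analyte at a time. The documents give no quantification limit and no rate for four quadrants, so both the rates and the example concentrations are assumptions.

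A reader might go further and infer that the conclusion on systemic exposure is at risk. It is not. Tmax is missing for an all-BLQ subject, so n for Tmax counts the subjects with a quantifiable level, and SAP 7.8.1 separately counts samples above the limit. No test, threshold or sample size depends on the geometric mean or CV.

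**What to change.** Reconcile SAP 6.3 with the protocol in one of two ways, stated per subject and per analyte:

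- **(a)** Determine PK parameters only for subjects with a quantifiable concentration, as the protocol Synopsis provides. This removes the zeros and needs no Table 12 entry. Arithmetic and geometric statistics for a parameter then start from the same subjects.
- **(b)** Keep the zeros for arithmetic statistics only. Record this in Table 12 and amend the statement in SAP 8 that no changes are planned.

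In both cases, state in SAP 7.8.2 that the geometric mean and CV use non-zero values only, that n is shown for each statistic, and that NC is printed where a statistic cannot be computed (geometric mean with no non-zero value, CV with fewer than two). Showing n matters for AUC0-inf in particular, since a terminal rate constant may not be estimable in every quantifiable subject. Also restate in the SAP that all PK parameters are NC when every subject is all BLQ.

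The cost is a few sentences, plus one Table 12 entry under (b); no new data or tables are needed. Option (b) has a further price: statistics in one row rest on different n, and the geometric mean can exceed the arithmetic mean, as in the example (17.0 on n = 4 against 6.08 on n = 12).

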6.3.1. Imputation of Partial Dates

6.3.1.1. TEAE Status for Completely Unknown Start Date

The following rules will apply in cases where start date of an AE is completely unknown:

- If the AE onset date is unknown and the end date is after first injection on Day 1 or ongoing, then the AE will be considered a TEAE.
- If the AE onset date is unknown and the end date is before first injection on Day 1, then the AE will not be considered a TEAE.
- If both the start and end dates are unknown (or end date is ongoing), then the AE will be considered a TEAE, following the worst-case principle.

If the AE onset date is partly present and month/year is prior to the first injection date then the AE will not be considered a TEAE.

6.3.1.2. Concomitant Status of Medication for Completely Unknown Start Date

The following rules will apply in cases where start date of concomitant medication is completely unknown:

- If the medication onset date is unknown and the end date is after first injection on Day 1 or ongoing, then the medication will be considered as concomitant.
- If the medication onset date is unknown and the end date is before first injection on Day 1, then the medication will not be considered as concomitant.
- If both the start and end dates are unknown (or end date is ongoing), then the medication will be considered as concomitant, following the worst-case principle.

If the medication onset date is partly present and month/year is prior to the first injection date, then the medication will not be considered as concomitant.

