16.6.1. Prior, Concomitant, and Follow-up Medication

The WHO Drug Dictionary will be used to classify prior and concomitant medications by therapeutic class. The version used in this study will be stated in the Data Management Plan. Prior medication will be defined as any medication with a start date prior to the Day 1 date and are collected at the Screening visit and upon admission to the clinic on Day –1. Concomitant medication is defined as any medication with a start date on or after the Day 1 date or reported as ongoing.

Prior and concomitant medication use will be summarized descriptively by the number and percentage of subjects receiving each medication within each therapeutic class. Multiple use of the same medication by a subject will be counted only once.

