4.3. Prior/Concomitant Medications

All medications will be coded using World Health Organization (WHO) Drug Dictionary by active ingredient and WHO anatomical therapeutic chemical (ATC) classification of ingredients.

A concomitant medication is defined as any medication given to the subject starting on or after the date of the first injection or the medication started prior to the date of the first injection but is reported as ongoing. A prior medication is any medication with a stop date prior to the date of the first injection.

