8. CHANGE FROM PROTOCOL

This SAP is prepared based on the study protocol dated September 07, 2018 and there are no planned changes either in the conduct of the study or planned analysis at the time of preparing this SAP.

[Table 12](#) lists any significant changes in the SAP from what is proposed in the protocol.

Table 12: Changes from Protocol

Text in Protocol	Change in SAP	Justification

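### Two SAP derivation rules are wrong as written (concomitant status with a partial start date; time since last EFP treatment), and the AE duration table cannot place events that are still open

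*SAP*

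**What the plan says.** **Medications.** SAP 4.3 counts as concomitant anything started on or after the first injection, and also the case where "the medication started prior to the date of the first injection but is reported as ongoing". It then says: "A prior medication is any medication with a stop date prior to the date of the first injection". Protocol 16.6.1 agrees on ongoing medications ("Concomitant medication is defined as any medication with a start date on or after the Day 1 date or reported as ongoing") but defines the other class by start date: "Prior medication will be defined as any medication with a start date prior to the Day 1 date". SAP 8 states that "there are no planned changes either in the conduct of the study or planned analysis", and its Table 12 of changes is empty.

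For a completely unknown start date, the first bullet of SAP 6.3.1.2 looks at the end: if "the end date is after first injection on Day 1 or ongoing, then the medication will be considered as concomitant". The closing sentence of that section covers a partial start date and looks only at the start: if it is "partly present and month/year is prior to the first injection date, then the medication will not be considered as concomitant".

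**EFP treatment.** Table 11 in SAP 6.2 defines the time since the last treatment as "Date of most recent EFP treatment – Date of informed consent)/365.25". The opening bracket is missing; I read it as the difference divided by 365.25. SAP 7.5 summarizes the result in years. SAP 6.3.1.3 imputes missing end days and months to the end of the month or year, except that an end date in the injection year goes to the first injection date.

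**AE duration.** Table 11 defines duration as end date minus start date plus 1. SAP 7.9.2 tabulates related TEAEs as under 14, 14 to 21 and over 21 days. SAP 6.3 imputes no safety data apart from AE relationship and severity. Protocol 14.5.1 lets follow-up of an open AE stop 14 days after the last visit.

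**The concern.** A programmer cannot satisfy both SAP 4.3 and the closing sentence of 6.3.1.2. Under that sentence, knowing the start month of an ongoing medication makes it non-concomitant, while knowing nothing about the start makes it concomitant. More information reverses the answer.

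The EFP variable has the opposite sign to its name. Reversing the subtraction alone would leave some imputed records negative.

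The duration table is meant to show how long related reactions last. The events that outlast follow-up are the ones it cannot place, although an event seen to be open for 22 days is known to belong in the top band. Safety is a primary objective, so the table should be able to show them.

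**Working it through.** The plan states no figure to reproduce here. I applied each rule literally. All dates and counts marked as assumed are illustrations.

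**1. Concomitant status** (assumed injection date 15 Oct 2018)

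| Medication | SAP 4.3 | SAP 6.3.1.2 | Protocol 16.6.1 |
|---|---|---|---|
| Start 'Jun 2018', ongoing | concomitant, not prior | not concomitant (closing sentence) | prior and concomitant |
| Start unknown, ongoing | not decided by start | concomitant (first bullet) | concomitant |
| Start 'Jun 2018', stopped before injection | prior | not concomitant | prior |
| Full start date before injection, stopped after it | not prior; concomitant only if 'ongoing' means at injection | no rule needed | prior; concomitant only on the same reading |

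The first row is the contradiction. If 6.3.1.2 overrides 4.3, that medication falls in 0 of the SAP's 2 classes. The third row shows where the closing sentence is harmless: the medication had already stopped.

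**2. Time since last EFP treatment**

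As written: (treatment date - consent date)/365.25. For a treatment 730 days before consent, -730/365.25 = -2.0 years. Reversed, it is +2.0.

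Imputation example (assumed): injection 15 Oct 2018, consent 23 Sep 2018 (Day -22), massage ended 'May 2018'. SAP 6.3.1.3 can be read in two ways.

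- The injection-year exception covers missing days too. The end date becomes 15 Oct 2018, 22 days after consent. As written, 22/365.25 = +0.060 years; with only the sign reversed, -0.060.
- The exception covers missing months only. The end date becomes 31 May 2018, 115 days before consent. As written, -115/365.25 = -0.315 years; reversed, +0.315.

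If only the year 2018 is known, both readings give 15 Oct 2018. Capping that at consent would enter 0 years. For massage or Endermologie this conflicts with exclusion 6, which requires 3 and 6 months respectively before injection.

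**3. Duration of open AEs**

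Minimum duration = last contact day - onset day + 1.

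- Contact to Day 22: onset Day 1 gives 22 - 1 + 1 = 22 (over 21); onset Day 2 gives 22 - 2 + 1 = 21.
- Contact to Day 36 (Day 22 + 14): onset Day 15 gives 36 - 15 + 1 = 22; onset Day 16 gives 36 - 16 + 1 = 21.

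So an open AE is certainly over 21 days for onset on Day 1, or on Days 1 to 15 with the full 14-day follow-up.

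SAP 6.1 names the number of subjects as denominator and, further on, the number with non-missing values. Assumed example: 9 of 12 subjects have a related term; 6 last under 14 days, 2 last 14 to 21 days, and 1 is open beyond 21 days.

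| Denominator | Under 14 | 14 to 21 | Over 21 |
|---|---|---|---|
| Non-missing, as written | 6/8 = 75.0% | 2/8 = 25.0% | blank |
| Non-missing, after fix | 6/9 = 66.7% | 2/9 = 22.2% | 1/9 = 11.1% |
| 12 Safety subjects, as written | 6/12 = 50.0% | 2/12 = 16.7% | blank |
| 12 Safety subjects, after fix | 50.0% | 16.7% | 1/12 = 8.3% |

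**The case against.** The fair reply is that nothing important turns on these rules. The sign error is an obvious transposition that would show at first output. Few EFP end dates should need the injection-year imputation, since exclusion 6 leaves mainly creams, massage and Endermologie. Protocol 10.2 reports that most AEs at 0.84 mg resolved before the next session, 21 days later, so long events may be rare. All of that stands and fixes the rating at minor. It does not make the wording right.

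Some stronger readings are tempting, and the documents do not support them:

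- *Medications will drop out of the SAP 7.6 summary.* That section does not say whether prior and concomitant medications share a table. In a combined table an unclassified record need not be lost. The layout is in Module 2, and the records stay in the listing in any case.
- *SAP 4.3 leaves medications stopped after injection in neither class.* This holds only if 'ongoing' means at study end. Read as ongoing at injection, they are concomitant. The wording needs clarifying; it is not a proven gap.
- *The SAP has no rule at all for open AEs.* It has a default: no imputation, and a displayed category for missing values. What is absent is a specific rule for events known to be ongoing, and Module 2 may contain one.
- *The shorter duration bands are inflated.* Only with the non-missing denominator. The later sentence in SAP 6.1 may be meant to specify the earlier one, but the table's denominator should be stated.
- *The AE overview row for no severe but at least one mild TEAE is an error.* It overlaps the moderate row for subjects with both grades, but it is accurate as labelled. A worst-grade split is a presentation preference, so I make no point of it.

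**Conclusion.** Two rules are wrong on their face. The closing sentence of SAP 6.3.1.2 contradicts SAP 4.3, protocol 16.6.1 and its own section for an ongoing medication with a partial pre-injection start. The Table 11 formula gives a negative value for every treatment dated before consent. Neither conclusion needs an assumption about the data.

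The third point is smaller: as far as the SAP text goes, a related AE open for more than 21 days can be shown only as missing and in the AE listing. That is conditional on Module 2.

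How many records are affected cannot be told from the documents; the dates and counts above are assumed. The effect is confined to the medication, EFP history and AE duration summaries of a 12-subject descriptive study. Separately, the SAP defines prior medication by stop date where the protocol uses start date, without recording the change.

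**What to change.** 1. **SAP 6.3.1.2 and 4.3.** Apply the closing sentence only when the medication also stopped before the first injection. State in 4.3 that a medication started before the first injection, and either stopped on or after it or still ongoing, is concomitant. Record in Table 12 that prior is now defined by stop date; under the protocol an ongoing pre-Day 1 medication is both prior and concomitant.
2. **Table 11 and SAP 6.3.1.3.** Use (consent date - treatment date)/365.25. For a partial end date in the injection year with a known month, impute the last day of that month, capped at the consent date. If the month is missing, leave the time since treatment missing in the summary and show the partial date in the listing; do not enter 0 years.
3. **AE duration.** Unless Module 2 already handles it, count an AE recorded as ongoing in the over-21-day band when last visit date (or later documented contact) minus onset date plus 1 exceeds 21. Otherwise show it in a separate ongoing row. State the table's denominator.

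The cost is SAP wording before programming. Point 3 can run on the last visit date, which Table 11 already uses, so it needs no new data field.
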